Title of the document	Clinical Research Protocol
Title of the study	Phase II, multi-center, randomized, double-masked clinical study to evaluate the safety and efficacy of the PRO-157 ophthalmic solution in three different posologies versus Moxifloxacin and versus Gatifloxacin in patients with bacterial conjunctivitis.
Study drug	Pazufloxacin
Indication	Antibiotic for the treatment of bacterial conjunctivitis
Development phase	Phase II
Protocol Code	SOPH157 - 0114 / II
Sponsor	Sophia Laboratories, S.A. of C.V.
Version 4	April 2016

1.- SUMMARY STUDY

Sponsor's name: Laboratorios Sophia, S.A. of C.V.	
Finished Product Name: NA	
Active Ingredient Name: Pazufloxacin	
Title of the study: Phase II clinical study, multicenter, randomized, double masked to evaluate the safety and efficacy of the ophthalmic solution PRO-157 in three different posologies versus Moxifloxacin and versus Gatifloxacin in patients with bacterial conjunctivitis.	
Study centers: To be defined	
Study period: 7 days	Phase of development of the study: Phase II
Objectives:	
General purpose:	
To evaluate the safety and efficacy of the ophthalmic solution PRO-157 in three different posologies versus Moxifloxacin and versus Gatifloxacin in patients with bacterial conjunctivitis.	
Specific objectives:	
To determine the safety of the PRO-157 solution in three different posologies versus Moxifloxacin and versus Gatifloxacin in patients with bacterial conjunctivitis by the incidence of adverse events.	
To evaluate the efficacy of the ophthalmic solution PRO-157 in three different posologies versus Moxifloxacin versus Gatifloxacin in patients with bacterial conjunctivitis through the evaluation of ocular signs and symptoms such as: burning, lacrimation, foreign body sensation, pruritus, photophobia, hyperemia conjunctival, chemosis, secretion, membranes and / or pseudomembranes, scales and palpebral edema, epitheliopathy.	
Work hypothesis	
The ophthalmic solution PRO-157 is so safe and effective in any of its different posologies when demonstrating non-inferiority when compared against Moxifloxacin and Gatifloxacin in the treatment of bacterial conjunctivitis.	
Ho: The ophthalmic solution PRO-157 is not as safe and effective in any of its different dosages when demonstrating non-inferiority when compared against Moxifloxacin and Gatifloxacin in the treatment of conjunctivitis	

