Ha: The ophthalmic solution PRO-157 is so safe and effective in some of its different posologies when demonstrating non-inferiority when compared against Moxifloxacin and Gatifloxacin in the treatment of conjunctivitis	

Sponsor's name: Laboratorios Sophia, S.A. of C.V.

Finished Product Name: NA

Active Ingredient Name: Pazufloxacin

Methodology

Multicentric double randomized study masked.

Number of participants: 300 eyes, 60 eyes per treatment group

Diagnosis and main criteria for inclusion

Patients with bacterial conjunctivitis (signs and / or symptoms and / or culture)

Subjects aged 0 years to 99 years.

Study medication:

Pazufloxacin

- **Treatment duration:**
- - **Recruitment period: 4 months**
- - **Period of treatment: 7 days**
- - **Period of follow-up: 15 days**

Criteria for evaluation:

Efficacy measurements:

Main efficacy criterion

It will be determined as effective if there is a reduction in the number or species of bacterial flora comparing the basal culture against the final between the five different groups of patients and / or if there is a reduction or absence of the infection with the clinical evaluation through signs and symptoms such as: burning, tearing, foreign body sensation, pruritus,

photophobia, conjunctival hyperemia, chemosis, secretion, palpebral edema, membranes and / or pseudomembranes, palpebral scales and epitheliopathy

Security measurements:

Visual ability

Adverse events

INDICE

1. Summary of the study	2
2. Glossary and definitions	6
3. Administrative structure of the study	7
3.1 Parties not sponsored.	7
3.2 Sponsored parties	8
4. Background information	8
4.1 Justification	9
4.2 Non-clinical pharmacology	11
5. Clinical Studies	17
6. Hypothesis and Objectives	17
6.1 Work hypothesis	17
6.2 Objectives.	19
7. Point or points limit	19
8. Study plan	25
9. Measures to minimize deviations	29
10. Products administered	30
11. Description of the packaging	31
12. Management of the study medication	31
13. Closure of the center	33
13.1 Premature discontinuation of study	31
13.2 Center closure	31
14. Source data	33
15. Selection and withdrawal of subject of study	33
15.1 Inclusion criteria	33
15.2 Exclusion criteria	34
15.3 Criteria for patient withdrawal	36
16. Treatment of the study subjects	37
16.1 Managed treatments	37
16.2 Delivery of treatment	37
16.3 Previous and concomitant treatments	37
16.4 Treatments authorized during the study	39
16.5 Drug compliance	39
17. Methods and times of measurements	39

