The pathogenesis usually involves the disruption of the ocular surface defense mechanisms, due to trauma, tear film dysfunction or palpebral abnormalities, etc.

Usually its installation occurs 1 to 2 days after contact, characterized by rapid appearance of clinical signs such as palpebral edema, hyperemia, mucopurulent secretion, membranes and / or pseudomembranes.

The main infectious agents in adults are *H. influenzae*, staphylococci and streptococci. *H. influenzae*, *S pneumoniae*, and *Moraxella catarrhalis* are the most frequent agents in children. The course of the clinical picture is 7 to 10 days long.

Due to its clinical presentation, it is convenient to divide them according to their installation time, in acute, acute or chronic hyperinflation, and can guide diagnostic tests and empirical treatment according to the time of presentation.

Common pathogens according to the time of evolution

Acute	Híper Acute	Chronic
Staphilococcus Aureus.	Neisseria Gonorreae.	Moraxella catarrhalis.
Streptococcus pneumoniae.	Neisseria meningitidis.	Moraxella Lacunata.
Haemophilus influenzae.		Enterobacterias.

Special conditions:

In sexually active subjects who do not give up the clinical picture with empirical treatment (ceftriaxone 1gr b.i.d), we should investigate *Chlamydia Trachomatis* and add the relevant treatment.

In the case of infants or minors (less than 2 years old), we should consider granting systemic treatment because 50% of them concur with infections in other systems.

In oculo-vaginal infections we must investigate on strains compatible with trachoma (A-C); since we must remember that it affects more than 40 million subjects in areas of poor hygiene and continues to be a leading cause in non-reversible blindness.

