6.2 Objectives

General purpose:

To evaluate the safety and efficacy of the ophthalmic solution PRO-157 in three different posologies versus Moxifloxacin and versus Gatifloxacin in patients with bacterial conjunctivitis.

Specific objectives:

To determine the safety of the PRO-157 solution in three different posologies versus Moxifloxacin and versus Gatifloxacin in patients with bacterial conjunctivitis by the incidence of adverse events and visual capacity.

To evaluate the efficacy of the ophthalmic solution PRO-157 in three different posologies versus Moxifloxacin and versus Gatifloxacin in patients with bacterial conjunctivitis through conjunctival cul-de-sac culture and the clinical evaluation of some ocular signs and symptoms such as: burning, lacrimation, Foreign body sensation, pruritus, photophobia, conjunctival hyperemia, chemosis, secretion, palpebral edema, membranes and / or pseudomembranes, scales and epitheliopathy.

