7 STUDY DESIGN

7.1 Point or limit points

Criteria for the evaluation.

Efficacy measurements:

Main efficacy criterion

Efficacy will be determined by taking cultures of the lower conjunctival cul-de-sac background quantifying (colony-forming units) and identifying genus and basal and final microbial species.

It will be determined as effective if there is a reduction in the number or species of bacterial flora comparing the basal culture against the end between the five different groups of patients and / or if there is a reduction or absence of the following specific signs and symptoms: burning, tearing, Foreign body sensation, pruritus, photophobia, conjunctival hyperemia, chemosis, palpebral edema and secretion, membranes and / or pseudomembranes when comparing the study medication versus Moxifloxacin and versus Gatifloxacin from baseline to final visit.

Efficiency parameters

- The effectiveness of the drug will be evaluated by means of:

1. Clinical referral

2. Microbiological remission

Clinical remission will be evaluated by means of the signs and symptoms that the patient presents at the beginning and at the end of the study.

Variable	Operationalization	Measurement scale	Value
Secretion	Dependent Qualitative ordinal	Absent Present	Must be recorded as absent in 95% of the subjects evaluated
Conjunctival hyperemia	Dependent Qualitative ordinal	Absent Mild Moderate Severe	You must comply with the following: • Absent \geq 95.0% • Mild \leq 5.0% • Moderate \leq 2.5% Severe \leq 1.0%
Chemosis	Dependent Qualitative ordinal	Absent Present	Must be recorded as absent in 95% of the subjects evaluated
Eyelid edema	Dependent Qualitative ordinal	Absent Present	Must be recorded as absent in 95% of the subjects evaluated
Corneal epithelial defects	Dependent Qualitative ordinal	Affected area, percentage	Percentage of affected area less than 95%

The microbiological remission will be evaluated by means of the culture taken from the conjunctival sac fundus.

Variable	Operationalization	Measurement scale	Value
Culture	Dependent Discrete quantitative	UFC * / ml Eradication Reduction Proliferation	Must be recorded as absent in 95% of the subjects evaluated

* Colony forming units

The drugs under study will be considered effective if the patient has any of the following:

1. Clinical remission + Microbiological remission.
2. Clinical referral.
3. Microbiological remission.

Security measurements:

Adverse events and visual capacity.

Evaluation parameters

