Eyelid edema	Dependent Qualitative ordinal	Absent Present	Must be recorded as absent in 95% of the subjects evaluated
Membranas Pseudomembranes	Dependent Qualitative ordinal	Absent Present	Must be recorded as absent in 95% of the subjects evaluated
Scales	Dependent Qualitative ordinal	Absent Present	Must be recorded as absent in 95% of the subjects evaluated

Epithelial defects corneal	Dependent Qualitative ordinal	Affected area, percentage	Percentage of the affected area 95%
Adverse events	Dependent Qualitative ordinal	serious Not Serious	Must be recorded as absent in 95% of the subjects evaluated

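### Section 7.1 judges clinical efficacy on ten signs and symptoms, but its clinical remission table has rows for only five signs, with no symptom and no membranes, and no per-patient rule links the two

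*Combined protocol and SAP*

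**What the plan says.** The clinical side of efficacy is described in four places in the protocol.

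- **Synopsis (section 1).** The efficacy objective lists "burning, lacrimation, foreign body sensation, pruritus, photophobia, hyperemia conjunctival, chemosis, secretion, membranes and / or pseudomembranes, scales and palpebral edema, epitheliopathy". The main efficacy criterion there repeats the same twelve items in another order, ending with "photophobia, conjunctival hyperemia, chemosis, secretion, palpebral edema, membranes and / or pseudomembranes, palpebral scales and epitheliopathy".
- **Section 6.2, Objectives.** Efficacy is to be assessed by culture and by "the clinical evaluation of some ocular signs and symptoms such as: burning, lacrimation, Foreign body sensation, pruritus, photophobia, conjunctival hyperemia, chemosis", and the list continues to the same twelve items.
- **Section 7.1, main efficacy sentence.** Effectiveness is a reduction in flora and/or a reduction or absence of a list introduced as specific. It has ten items; scales and epitheliopathy are not among them.
- **Section 7.1, efficacy parameters.** The lead-in reads "Clinical remission will be evaluated by means of the signs and symptoms that the patient presents". The table below it has rows for secretion, conjunctival hyperemia, chemosis, eyelid edema and corneal epithelial defects. The next text is the microbiological definition.

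Section 7.1 then counts a treatment as effective if the patient has clinical remission, microbiological remission, or both.

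The items missing from the remission table have thresholds only in the safety table of section 7.1, for example the row "Membranas Pseudomembranes". Pruritus is named in the safety parameter list (as itching) but has a row in neither table.

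**The concern.** Within one section, the criterion and the table that should put it into operation use different items. The table is the only place where clinical remission is given items and values, so whoever programs the endpoint would naturally start there. Doing so drops all five symptoms and membranes from the efficacy result, although the sentence above the table counts them and section 4.1 describes bacterial conjunctivitis by "clinical signs such as palpebral edema, hyperemia, mucopurulent secretion, membranes and / or pseudomembranes".

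Clinical remission is sufficient for success on its own, so the item list directly affects who is counted. If it is left open, the list can be chosen after the data are seen. The trial states a non-inferiority hypothesis, and the plan should not leave that choice open for a component of its main efficacy criterion.

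**Working it through.** The main check is a comparison of item sets. Tearing is matched with lacrimation, palpebral with eyelid edema, and epitheliopathy with corneal epithelial defects.

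| Item | Synopsis and 6.2 | 7.1 sentence | 7.1 remission table |
|---|---|---|---|
| Burning | yes | yes | no |
| Tearing | yes | yes | no |
| Foreign body sensation | yes | yes | no |
| Pruritus | yes | yes | no |
| Photophobia | yes | yes | no |
| Conjunctival hyperemia | yes | yes | yes |
| Chemosis | yes | yes | yes |
| Secretion | yes | yes | yes |
| Eyelid edema | yes | yes | yes |
| Membranes/pseudomembranes | yes | yes | no |
| Scales | yes | no | no |
| Epitheliopathy/corneal epithelial defects | yes | no | yes |
| **Count** | **12** | **10** | **5** |

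The table is not a subset of the sentence: it drops six of the ten items and adds one the sentence lacks (10 − 6 + 1 = 5).

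**What the table permits.** Take a patient with no secretion, hyperemia, chemosis or eyelid edema, and with any epithelial defect covering less than 95% of the area, which is the value in that row. Read patient by patient, every row is met. Membranes and all five symptoms may be present, because no row refers to them. This reading has to be supplied: four of the five rows are written as percentages of subjects, and no passage says how rows combine for one patient.

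**Illustrative size.** The protocol gives no item-level rates, so these inputs are assumptions: each item is absent at the final visit with probability p = 0.95 or 0.90, and items share one latent normal factor with correlation ρ = 0, 0.3 or 0.6. The probability that all k items are absent is

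P(k) = ∫ φ(z) · Φ((Φ⁻¹(p) − √ρ·z)/√(1−ρ))ᵏ dz,

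which is pᵏ when ρ = 0. For example, 0.95⁵ = 0.774 and 0.95¹² = 0.540.

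| p | ρ | 5 items | 10 items | 12 items | 5 minus 12 (points) |
|---|---|---|---|---|---|
| 0.95 | 0 | 77.4% | 59.9% | 54.0% | 23.3 |
| 0.95 | 0.3 | 80.7% | 69.3% | 65.8% | 14.9 |
| 0.95 | 0.6 | 84.9% | 78.4% | 76.5% | 8.4 |
| 0.90 | 0 | 59.0% | 34.9% | 28.2% | 30.8 |
| 0.90 | 0.3 | 66.0% | 50.5% | 46.3% | 19.7 |
| 0.90 | 0.6 | 73.3% | 64.2% | 61.8% | 11.6 |

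This covers the clinical component only. Microbiological remission alone is also success, so if it occurs with probability m, independently of clinical remission, the gap in overall success is (1 − m) times the gap above. With the 69.8% absolute efficacy that section 23 uses for treated patients, 1 − m = 0.302, which gives 0.302 × 8.4 = 2.5 to 0.302 × 30.8 = 9.3 points.

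**The case against.** Several points on the other side stand.

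- The twelve-item lists are introduced as examples and never use the term remission, so they do not set up a rival definition of it. The firm conflict is inside section 7.1, between a list called specific and the table beneath it.
- The remission table is not declared exhaustive, its lead-in mentions symptoms, and most of its values are group percentages. A reader might infer that the protocol actually scores a patient with membranes and every symptom as remitted. It does not say that; it only fails to prevent it under a reading it never writes.
- A reader might also infer that the trial cannot answer its objective on symptoms and membranes. The documents do not support that. Section 18.2 schedules all twelve items at every study visit, section 23 has each variable described in the intention-to-treat population, and the section 7.1 sentence itself compares the symptoms and membranes between drugs.
- It is tempting to say that symptoms have been moved out of efficacy and into safety. The five remission signs are in the safety table too, and the phase I study used burning, foreign body sensation and lacrimation as tolerability measures. Whether these items stay in the safety table is a separate question.
- The percentages above score complete absence and treat corneal defects as present or absent. The criterion sentence accepts reduction, and the table row accepts any area below 95%. The figures therefore model neither text exactly and are not bounds.
- A signs-only definition is defensible: three of the four signs named in section 4.1 are already in the table.

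None of this removes the mismatch. Even if a signs-only definition was intended, the criterion sentence says otherwise.

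**Conclusion.** The inconsistency is established on the text and needs no assumption: ten items in the section 7.1 sentence, five in its remission table, no symptom and no membranes in the table, and twelve in the illustrative lists elsewhere. That a patient with membranes and all five symptoms could count as remitted is conditional on using the table as the definition and reading it as a patient-level rule.

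The size is illustrative: about 8 to 31 points between five-item and twelve-item complete absence in the clinical component, and about 2.5 to 9.3 points in either/or success under the further assumption of independence and 69.8% eradication. A shorter list raises remission in any arm, and a reader might infer bias in the comparison with moxifloxacin or gatifloxacin; no between-arm effect has been shown. This should be corrected before analysis because it concerns a component of the main efficacy criterion.

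**What to change.** 1. Reconcile the synopsis, section 6.2, the section 7.1 sentence and the section 7.1 remission table into one pre-specified item list. It should include the five symptoms and membranes that the section 7.1 sentence already names, and say explicitly whether scales and corneal epithelial defects count.
2. State how the items combine into clinical remission for each patient, including whether reduction is enough or absence is required. Without this, an agreed list still does not determine who is remitted.
3. Give pruritus a row and a scale. It has a row in neither table, and section 17 gives it no scale. If scales are kept, add them to the key of the section 8 timeline, which omits them.
4. Report the five-sign version as a sensitivity result.

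No new visit or examination is needed, since section 18.2 already schedules every item; the cost is mostly wording, plus one scale. The downside is that the stated remission rate may be lower.

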4.1 JUSTIFICATION

Conjunctivitis and bacterial keratitis are the pathologies of the ocular surface most commonly found in our environment. In general, they resolve spontaneously, however if they are not treated properly they can have irreversible consequences for visual health

(corneal ulcers, endophthalmitis, etc.), especially in patients who will be operated on ophthalmic surgery and / or senile, children, contact lens wearers, among others.

These pathologies do not respect age, gender or social status. They are transmitted through contact with flush when talking to an infected person or through touch - hand - eye. Hence, it is quite common. The acute form of the infection is usually caused by *Haemophilus* species, *S. pneumoniae*, *S. aureus* or *epidermidis*, some of them normal habitual residents of the human conjunctiva.

Its management, sometimes represents a diagnostic and therapeutic challenge for both the general practitioner and the ophthalmologist. The etiology of it is a very useful guidance to improve the patient's prognosis. Much of the morbidity produced by this pathology can be lessened with adequate therapy by reducing treatment time and comfort. Hence the importance of knowing the ocular pathogens commonly associated with our environment, isolating them in an accurate manner and correlating them with the specific characteristics of the patient.

There are innumerable reports in the literature in this regard, however we have no knowledge of a specific one in our geographical area. The prevalence of *Staphylococcus aureus* 80 (23.7%), *Staphylococcus albus* 65 (19.2%), *Pseudomonas aeruginosa* 34 (10.1%), *Streptococcus pneumoniae* 29 (8.6%), *Haemophilus influenzae* 26 (7.7%), *Streptococcus pyogenes* 20 has been recently published. (6.2%), *Klebsiella pneumoniae* 18 (6.2%) *Escherichia coli* 15 (4.4%), *Neisseria gonorrhoeae* 13 (3.9%), *Streptococcus viridans* 11 (3.5%), *Moraxella catarrhalis* 10 (3.0%), among others, found that The most frequent isolations were made from the conjunctiva (66.7%) in contrast to the cornea (20.1%). These data correspond to the majority of what is published, however the socioeconomic and environmental conditions of the place where they were carried out are not the same to our region.

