16 TREATMENT OF STUDY SUBJECTS

16.1 Managed treatments

Lagricel Ofteno® Apply one drop 4 times a day for 7 days + any of the following according to the randomization in both eyes.

Apply one drop of PRO157, 2 TIMES a day, from day 1 to day 7
Apply one drop of PRO157, 3 TIMES a day, from day 1 to day 7
Apply one drop of PRO157, 4 TIMES a day, from day 1 to day 7
Apply a drop of Moxifloxacin, 3 TIMES a day, from day 1 to day 7
Apply a drop of Gatifloxacin, 3 TIMES a day, from day 1 to day 7

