23. STATISTICS

Sample size

We conducted a review of published articles regarding the use of medications in the treatment of bacterial conjunctivitis. We found three publications that are the following:

- 1) "Gatifloxacin Ophthalmic Solution for Treatment of bacterial Conjunctivitis: Safety, Efficacy and Patient Perspective". Clyde Schultz. En Ophthalmology and Eye Diseases. 2012:4 65-70.
- 2) "Microbiological Efficacy of a New Ophthalmic Formulation of Moxifloxacin Dosed Twice-Daily for Bacterial Conjunctivitis". Shachar Tauber et.al. En Adv Ther. (2010) 28(7):566-574.
- 3) "Clinical use of gatifloxacin ophthalmic solution for treatment of bacterial conjunctivitis". Lorenzo J. Cervantes y Francis S. Mah. En Clinical Ophthalmology. 2011:5 495.502.

The first of the publications referred to here (Clyde Schultz) is a review article that summarizes the findings regarding the use of gatifloxacin mainly as a treatment for bacterial conjunctivitis but does not give precise figures, it only says, for example, that the Effectiveness reported in an article made in China was around 93%. It is not an original article that gives specific results, but rather comments findings and issues an opinion regarding the convenience of using them as an effective and safe treatment for bacterial conjunctivitis.

The second revised article (Schachar Tauber) is an original article. This is a multicentre study in which 1180 patients were recruited throughout the United States of America, who had a clinical diagnosis of bacterial conjunctivitis. All patients were given a sample

prior to treatment and another at the end of treatment, which were sent to the clinical laboratory where standard methods of microbiology were used to isolate the biological specimens before and after the treatments. One group was treated with MOXI-AF and the other with placebo (vehicle) instilling in the conjunctival sac one drop twice a day for three days and the most important results of this investigation are summarized in Table 1.

The third article reviewed (Cervantes) describes other studies conducted to test gatifloxacin in two presentations: Zymar (0.3%) tested in 52 patients treated for three days vs. placebo (vehicle) tested in 48 patients and Zymaxid (0.5%) tested in 333 patients for three days vs. placebo (vehicle) tested in 325 patients for three days.

The results reported in these articles regarding efficacy can be summarized in Table 1.

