Cuadro 1. Eficacia de medicamentos para erradicación de bacterias en infecciones oculares (Conjuntivitis) reportada en publicaciones.

Tratamiento	Eficacia Absoluta	Total ojos		Eficacia %
		n	n	
MOXI-AF¹		424	316	74.53%
Placebo (Vehículo)¹		423	237	56.03%
Zymar²		52	40	76.92%
Placebo (Vehículo)²		48	28	58.33%
Zymaxid²		333	193	57.96%
Placebo (Vehículo)²		325	148	45.54%

Tratamiento	Eficacia específica por bacteria			
MOXI-AF¹	Haemophilus influenzae	67	66	98.51%
	Streptococcus pneumoniae	22	19	86.36%
	Staphylococcus aureous	17	16	94.12%
Placebo (Vehículo)¹	Haemophilus influenzae	52	31	59.62%
	Streptococcus pneumoniae	18	9	50.00%
	Staphylococcus aureous	15	12	80.00%
Zymar²	*	52	48	92.31%
Placebo (Vehículo)²	*	48	34	70.83%
Zymaxid²	*	333	301	90.39%
Placebo (Vehículo)²	*	325	228	70.15%

* **Nota:** La eficacia específica por bacteria en los estudios con Zymar y con Zymaxid no se presenta para cada bacteria sino para la totalidad de bacterias que aparecieron en el cultivo inicial y ya no aparecieron en el cultivo post-tratamiento.

¹ Microbiological Efficacy of a New Ophthalmic Formulation of Moxifloxacin Dosed Twice-Daily for Bacterial Conjunctivitis. Shachar Tauber et.al. En Adv Ther. (2010) 28(7):566-574.

² Clinical use of gatifloxacin ophthalmic solution for treatment of bacterial conjunctivitis.

Lorenzo J. Cervantes y Francis S. Mah. En Clinical Ophthalmology. 2011:5 495-502.

To calculate the sample size, we obtained the overall average of absolute efficacy for patients treated with some medication and for patients treated with placebo. For patients treated with medication, the absolute efficacy (total disappearance of bacteria in the post-treatment culture) was 69.8% and for those treated with placebo it was 53.3%. The specific efficacy (disappearance of a specific bacterium that was present in the pre-treatment culture) for the groups treated with some medication was 92.34% and for patients treated with placebo 66.12%.

With these figures, we can calculate the sample size needed to detect that level of differences reported between patients with bacterial conjunctivitis treated with medication vs. patients treated with placebo.

Annex 1 develops the calculations for the sample size necessary to detect the differences in the percentage of efficacy to eliminate bacteria from patients with bacterial

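### The 95% culture-absent mark for microbiological remission has no stated basis, fits neither the per-patient rule around it nor the comparative hypothesis, and gives opposite verdicts on the comparators depending on what absent means

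*Combined protocol and SAP*

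**What the plan says.** Section 7.1 splits efficacy into clinical and microbiological remission. In the culture row the scale is CFU/ml with three categories (eradication, reduction, proliferation), and the required value is "Must be recorded as absent in 95% of the subjects evaluated". The decision rule after the tables reads "The drugs under study will be considered effective if the patient has any of the following", followed by three options: both remissions, clinical alone, or microbiological alone. The main criterion at the head of the section also accepts a mere reduction in the number or species of bacteria against baseline.

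Section 6.1 poses a non-inferiority hypothesis against moxifloxacin and gatifloxacin. The summary sets the size at "300 eyes, 60 eyes per treatment group".

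Section 23 tabulates two eradication measures from published studies. For the first, "the absolute efficacy (total disappearance of bacteria in the post-treatment culture) was 69.8" per cent on average with drug. The second is disappearance of a bacterium present before treatment, and its average "for the groups treated with some medication was 92.34" per cent. The plan calculates a sample size for each measure (147 and 44 per group) and does not say which one the 95% mark uses.

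**The concern.** The mark raises three problems.

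- **No basis.** Nothing in the plan supports 95%, and the average on either measure in section 23 is below it.
- **Wrong level.** A percentage of subjects is a property of an arm. It cannot tell the analyst whether one patient is in microbiological remission, which is what the decision rule needs.
- **Wrong question.** A pass mark for a single arm says nothing about PRO-157 relative to its comparators.

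The row also conflicts with its surroundings: the scale and the main criterion recognise reduction, but the value accepts only absence. If absence means no growth of anything, resident flora count against the drug. Section 4.1 (Justification) says of the usual causal species that they are "some of them normal habitual residents of the human conjunctiva" in some cases.

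At stake is whether an arm as good as the marketed controls would be denied microbiological remission, which would leave the efficacy conclusion to rest on the clinical component.

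**Working it through.** **Inputs from the section 23 table**

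- Total disappearance (absolute efficacy): MOXI-AF 316/424 = 74.53%; Zymar (gatifloxacin 0.3%) 40/52 = 76.92%; Zymaxid (gatifloxacin 0.5%) 193/333 = 57.96%.
- Baseline organism cleared (specific efficacy): MOXI-AF 66/67, 19/22 and 16/17 for three species; Zymar 48/52 = 92.31%; Zymaxid 301/333 = 90.39%.
- Eyes per arm: 60 (summary and section 8).

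**Step 1. The plan's averages reproduce as simple means.**

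- Absolute: (74.53 + 76.92 + 57.96)/3 = 69.8%.
- Specific: (98.51 + 86.36 + 94.12 + 92.31 + 90.39)/5 = 92.34%.

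Pooling the three moxifloxacin species gives (66 + 19 + 16)/(67 + 22 + 17) = 101/106 = 95.3%.

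**Step 2. Chance that an arm meets the mark.** The requirement is 0.95 × 60 = 57 eyes. With independent eyes and true rate p,

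P(X ≥ 57) = Σ (k = 57 to 60) C(60, k) p^k (1 − p)^(60 − k).

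| Reading of absent | Product | p | Expected eyes (60p) | P(X ≥ 57) |
|---|---|---|---|---|
| Total disappearance | MOXI-AF | 74.53% | 44.7 | 3.5 in 100,000 |
| Total disappearance | Gatifloxacin 0.3% | 76.92% | 46.2 | 1.6 in 10,000 |
| Baseline organism | Gatifloxacin 0.3% | 92.31% | 55.4 | 0.31 |
| Baseline organism | MOXI-AF, pooled | 95.3% | 57.2 | 0.69 |
| Either | Drug truly at the mark | 95% | 57.0 | 0.65 |

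The last row means a drug that truly meets the standard fails with probability 1 − 0.65 = 0.35.

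**Step 3. Sensitivity to the 3-day source data.** The published moxifloxacin course was "one drop twice a day for three days"; this trial's is "Apply a drop of Moxifloxacin, 3 TIMES a day, from day 1 to day 7", with the final culture on day 8. The documents give no 7-day rate. For illustration only, a true rate of 85% gives 1.5%, 90% gives 14% and 92% gives 28%.

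**Step 4. Sensitivity to the denominator.** Section 15.1 does not require a positive baseline culture. Suppose a share f of eyes is negative at baseline, stays negative and counts as absent. The expected proportion absent is then f + (1 − f)p, and it reaches 95% when f = (0.95 − p)/(1 − p):

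- p = 76.92%: f = 0.1808/0.2308 = 78%.
- p = 74.53%: f = 0.2047/0.2547 = 80%.
- p = 92.34%: f = 0.0266/0.0766 = 35%.

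The documents do not give f. An arm that passed this way would be showing its case mix, not drug effect.

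**The case against.** A reader might infer that the mark contradicts the plan's own table and that every arm, controls included, is bound to fail it. The documents do not support that, for these reasons:

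- **Absent is not defined as total disappearance.** The row lists eradication as a category, and section 7.1 identifies genus and species at both visits. Clearance of the baseline organism is a plausible reading, and on it pooled moxifloxacin is more likely than not to pass.
- **The lowest figure belongs to another product.** Section 23 names Vigamoxi and Zymar as the comparators. The 57.96% is Zymaxid, which also pulls down the 69.8% average. MOXI-AF, too, goes by a different name from the moxifloxacin product listed for this trial.
- **The rates may not transfer.** They come from 3-day courses, and the table has no PRO-157 rate.
- **The mark can discriminate on one reading.** At the 66.12% specific rate for placebo, the chance of 57 of 60 is about 8 in 100 million, against 31% to 69% for the two products above.
- **The consequence is limited.** Clinical remission alone is enough for a drug to count as effective, and the main criterion already mentions comparison with both controls.
- **Units differ.** The row counts subjects and the calculation counts eyes. Two eyes of one patient are not independent, which would widen the distribution and change the probabilities, though not the expected counts of 44.7 and 46.2.

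All of this stands, and it rules out the stronger inference. It does not supply a basis for 95%, a definition of absent, or a way to apply a group percentage to a patient.

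**Conclusion.** The concern holds as a defect in how the endpoint is specified. The 95% mark is unjustified, sits at the wrong level and does not address the hypothesis in section 6.1. Read as total disappearance, it is practically out of reach at the rates cited for the moxifloxacin and gatifloxacin 0.3% products. Read as clearance of the baseline organism, passing is less likely than not for gatifloxacin 0.3% and more likely than not for moxifloxacin. An undefined word should not decide between those outcomes.

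The sizes assume 60 independent eyes per arm, all culture-positive at baseline, and published 3-day rates carried over to 7 days. Extending them to PRO-157 assumes it behaves like the comparators. The documents do not establish that all arms will fail, or that an arm missing the mark would be called ineffective. The sponsor should correct the row before analysis.

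**What to change.** - Delete the 95% value from the culture row in section 7.1.
- Define microbiological remission for one stated unit (eye or subject) as eradication, on the final culture, of the pathogen or pathogens isolated at baseline.
- Use baseline-culture-positive eyes as the denominator, or subjects if that is the unit chosen.
- Do not restrict the definition to the organism list in section 17. That list only asks the laboratory for special attention, and it omits *Neisseria meningitidis* and *Moraxella lacunata*, both named as common pathogens in section 4.1 (Introduction). Do not count newly grown organisms as failure.
- Report the proportion per arm with its confidence interval, and judge PRO-157 by its difference from each comparator with a confidence interval. Write this into section 23, which currently says nothing on the threshold. The plan states no non-inferiority margin, so a formal non-inferiority conclusion would also need one.

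**Cost.** One table row and a short new paragraph in section 23. No new data are needed, because genus and species are already identified at both visits. The sponsor gives up a simple absolute mark and accepts a smaller, culture-positive denominator, so the intervals will be wider than with all 60 eyes.
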